7. RESEARCH QUESTION AND OBJECTIVES

Table 1 shows the objective of this study with some specifications.

Table 1. Primary and secondary research questions and objective.

Objective:	To compare direct and indirect estimations of prevalence of some rare, chronic diseases
Hypothesis:	No hypothesis is tested
Population:	Total population in the databases
Diseases: Cystic fibrosis Haemophilia (A and/or B) Pulmonary arterial hypertension Pancreatic cancer Sickle cell disease	
Setting:	3 databases with Electronic Healthcare Records from primary care
Main outcome:	Direct and indirect estimated prevalences

A. Primary research question and objective.

8. **RESEARCH METHODS**

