8.6 Study size

No sample size has been calculated.

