8.8.3. Point prevalence

The R package *IncidencePrevalence* will be used to estimate complete point prevalence.

Point prevalence will be estimated for January 1 of each calendar year during the study period. Denominator is the total number of persons in observation at the specific time point. All persons with a diagnosis before the time point and in observation in the database at this time point contribute to the numerator. Point prevalences will be plotted against calendar year. The point prevalence at 01/01/2016 will be used for the comparison with the indirect estimated prevalence.

In **Figure 1** some patients are shown with their observation period and time of first diagnosis relative to the study period. The observation period of patient 1 includes the time point for the point prevalence at 01/01/2016. Therefore, this patient contributes to the denominator for the point prevalence. First diagnosis of this patient is before 01/01/2016 (and even before the study period and before the patient's observation period), so this patient also contributes to the numerator. Likewise, patient 2 is in observation at 01/01/2016 and is diagnosed before, so this patient also contributes to both the denominator and numerator. For patient 3, 01/01/2016 falls within the observation period and therefore this patient contributes to the denominator only. The date of first diagnosis for patient 3 is after 01/01/2016, so this patient does not contribute to the numerator for point prevalence. The observation period of patient 4 ends before 01/01/2016. Hence this patient does not contribute to the denominator nor the numerator.

The estimate of the point prevalence will be reported with 95% confidence intervals (CI) using Wilson score method.

[figure not shown]

Figure 1 Diagram with patient data to illustrate incidence and prevalence calculations.

Dissemination level: Public

While the complete point prevalence estimated at the mid-point of the study period (January 1st 2016) will be used to compare with the indirect estimate of prevalence, estimates of complete point prevalence on January 1st of every year of the study period will also be reported to describe potential trends over time.

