8.8.6. Indirect estimated prevalence

From the overall incidence (I) and median disease duration (D) the indirect prevalence will be calculated with formula

$$P = I \cdot D \tag{1}$$

A CI for this indirect estimated prevalence will be generated by using the relation on the log scale:

$$\log P = \log(I \cdot D) = \log I + \log D \tag{2}$$

hence for the variance

$$Var(\log P) = Var(\log I) + Var(\log D) + 2 \cdot Cov(\log I, \log D)$$
(3)

This will be calculated using

$$Var(\log I) = 1/C \tag{4}$$

where C is the total number of cases used for the calculation of the incidence I.

An approximation of $Var(\log D)$ will be generated using the limits D_{low} and D_{upp} of the 95% CI for D:

$$Var(\log D) = \left(\left(\log D_{upp} - \log D_{low} \right) / (2 \cdot 1.96) \right)^2$$
(5)

We will assume incidence rate and disease duration are independent, hence

$$Cov(\log I \cdot \log D) = 0 \tag{6}$$

With the obtained variance of $Var(\log P)$ a 95% CI for $\log P$ will be calculated and then converted to a CI for *P*.

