8.9 Evidence synthesis

Estimated direct prevalence, incidence and median survival will be reported separately for each database. In addition, the results will be combined across data sources. To this end, a random-effect meta-analyses model will be fitted for all the results described below:

- 1. The direct estimated point prevalence. This will be done using the function metaprop of the R *meta* package using as input the numerators and denominators utilised to calculate the point prevalence in each database.
- 2. The incidence rate. For this meta-analysis, function metarate of the *meta* R package will be used with input the total number of events and the total number of person years in each database.
- 3. The median disease duration. For this meta-analysis, the function metagen of the *meta* R package will be used. Depending on the skewness of the CIs of the medians *D*, meta-analysis will be performed on log*D*. Input will be the estimates and the approximated standard errors calculated as described above in 8.8.6. equation (5).
- 4. The indirect estimated prevalence. For this meta-analysis, function metagen of the *meta* R package will be used. Meta-analysis will be performed on log*P*. Input will be the estimates and the approximated standard errors calculated as described above in 8.8.6. equation (3).

Forest plots and measures of statistical heterogeneity between data sources will be reported in addition to the combined results of the quantities of interest listed above.

For each of the results in 1) to 4) above, it might be that not all databases provide an estimate, for example, because the number in a numerator might be below the minimum value of 5 or the median disease duration might not be observed in the available data. Meta-analysis will be done with estimates available.

Finally, we will also calculate an indirect prevalence using the combined results for incidence and median disease duration.

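### The pooled direct and indirect prevalences may come from different sets of databases, so comparing them mixes between-country differences with disagreement between methods

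*Protocol*

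**What the plan says.** The single objective in section 7 is "To compare direct and indirect estimations of prevalence of some rare, chronic diseases", and the same table states "No hypothesis is tested". Section 8.8.3 names the direct estimate to be used: "The point prevalence at 01/01/2016 will be used for the comparison with the indirect estimated prevalence". Section 8.8.6 builds the indirect estimate in each database as incidence times median duration. Its confidence interval takes the variance of log D from the two confidence limits of D (equation 5).

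Section 8.9 then sets up four separate poolings: metaprop for direct prevalence, metarate for incidence, and metagen for median duration and for indirect prevalence. It recognises that a database may be absent from any of them, because a numerator is below 5 or the median is not observed, and rules "Meta-analysis will be done with estimates available". It closes with "Finally, we will also calculate an indirect prevalence using the combined results for incidence and median disease duration". Nothing requires the same databases in each pool. No ratio or difference of indirect to direct prevalence is defined, within a database or pooled. Section 8.7 does say that results are reported by database, and 8.9 adds forest plots and heterogeneity measures.

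**The concern.** Direct prevalence and incidence need no observed median; duration and indirect prevalence do. Through equation 5 the indirect estimate also needs a finite upper limit for D before it can be weighted. Section 8.2 says that no source offers lifelong observation, and follow-up is censored at deregistration or at the end of 2022. So for some diseases a database may well drop out of two of the four pools.

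The pooled direct figure then averages three countries and the pooled indirect figure averages one or two. A gap between them can arise because the countries differ, even if the methods agree in each. A real gap can likewise shrink or grow. Pooled incidence times pooled duration has the same weakness, since its two factors can come from different databases. For a study whose only purpose is to compare the methods, this blurs the quantity of interest.

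**Working it through.** The protocol states no expected prevalence, precision or sample size, so there is no figure of its own to reproduce. The check uses assumed examples.

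**Inputs.** From section 8.2, Table 3: 3.0, 1.3 and 5.8 million active subjects (UK, Netherlands, Spain), used as denominators. Assumed: the prevalences per 100,000 and the standard errors of log indirect prevalence shown below. In examples 1, 2 and 4 indirect equals direct in every database, so the true ratio is 1.00.

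**Method.** DerSimonian-Laird on the log scale, as an approximation to metaprop and metagen. The variance of log direct prevalence is 1/count; for indirect prevalence it is SE². Weights are 1/(variance + τ²). The direct pool uses all three databases.

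**1. Mild spread: 6/5/4 per 100,000, SE 0.15 each.** Counts are 6 × 30 = 180, 5 × 13 = 65 and 4 × 58 = 232; pooled direct is 4.92. With equal SEs the indirect pool is a geometric mean.

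| Database lost from indirect pool | Pooled indirect | Apparent ratio |
|---|---|---|
| UK | √(5 × 4) = 4.47 | 0.91 |
| Netherlands | √(6 × 4) = 4.90 | 1.00 |
| Spain | √(6 × 5) = 5.48 | 1.11 |

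If only one database remains, the ratio is 1.22 (UK) or 0.81 (Spain).

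**2. Fourfold spread: 20/10/5, SEs 0.15, 0.40, 0.10.** Counts are 600, 130 and 290; pooled direct is 10.0 (4.0 to 25.3).
- All three databases in the indirect pool: 10.0 (3.5 to 28.6), ratio 1.00.
- UK lost: variances 0.16 and 0.01, τ² = 0.155, weights 1/0.315 = 3.17 and 1/0.165 = 6.06. Pooled indirect is exp[(3.17 × ln 10 + 6.06 × ln 5)/9.23] = 6.3 (3.3 to 12.1), ratio 0.63.
- Spain lost: variances 0.0225 and 0.16, τ² = 0.149, pooled indirect 15.6 (8.1 to 29.9), ratio 1.56.
- Paired log ratio over all three: 1.00 (0.84 to 1.19).

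Part of this range comes from unequal weights. With SE 0.15 throughout, the ratios are √(10 × 5)/10.0 = 0.71 and √(20 × 10)/10.0 = 1.41. Conversely, with the UK lost, direct prevalence pooled over the same two databases is 7.05 against 6.35 for indirect. A common set alone does not guarantee equality.

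**3. All databases present, indirect half of direct: 12/8/4, SE 0.15.** Pooled direct is 7.27 (3.52 to 15.00) and pooled indirect 3.63 (1.94 to 6.81). The point ratio is 0.50, as it should be, but the intervals overlap. The paired ratio is 0.50 (0.41 to 0.60).

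**4. Pooled incidence times pooled duration.** Assume I = 1.2/1.0/0.8 per 100,000 person-years and D = 10/8/5 years, equal weights. The products are 12, 8 and 4, for which pooled direct is 7.27. Pooled I is (1.2 × 1.0 × 0.8)^(1/3) = 0.986.
- Spain lost from D: 0.986 × √80 = 8.82, ratio 1.21.
- UK lost: 0.986 × √40 = 6.24, ratio 0.86.
- D from the UK only: 9.86, ratio 1.36. D from Spain only: 4.93, ratio 0.68.

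**5. If the longest median is the one lost.** For assumed medians of 10, 14 and 20 years with equal weights, pooled D falls from 14.1 to √140 = 11.8, that is 16%.

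The paired intervals add the two variances as if independent. They are illustrative, because the two estimates share patients.

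**The case against.** Several points on the other side are sound.

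- **Pooling is an addition.** Section 8.7 reports every database separately, and forest plots would show which one is missing. A reader can compare within a database. This softens the harm, but leaves a comparison by eye with no stated measure of agreement. The opening sentence of 8.9 does not list indirect prevalence among the results reported by database.
- **The examples are assumed.** In the fourfold example the reduced-set intervals (3.3 to 12.1 and 8.1 to 29.9) both overlap the direct one (4.0 to 25.3). A reader who looks at the intervals would not conclude that the methods disagree; it is the point estimates that move.
- **No overlap criterion is planned.** The protocol nowhere says that overlapping intervals will be read as agreement. Example 3 shows what the separate intervals contain, not a planned error.
- **The choice of agreement measure is often left to an analysis plan**, which may exist unseen. That is fair for the missing ratio taken alone. The rule of pooling whatever is available, and the product of pooled components, are fixed in the protocol.

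A reader might also infer that medians go missing because survival is long, so that pooled duration must be too low. The documents do not support that certainty: a median can be unreached because follow-up is short, and estimates can be lost through small counts. Databases with longer survival relative to follow-up are more likely to drop out, which would lower pooled D, but that is a tendency only.

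**Conclusion.** The concern holds as a weakness of the stated pooling rule. When a median or its upper limit is unavailable in some databases, the pooled direct and indirect figures, and the product of pooled incidence and pooled duration, are not like for like. Under exact agreement, losing one of three databases shifts the apparent ratio to about 0.91 to 1.11 with mild spread and 0.63 to 1.56 with fourfold spread. These ranges rest on assumed prevalences and standard errors and an approximate pooling method, and the direction is not fixed.

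Two stronger readings should be resisted. One is that the plan will hide a twofold gap. In the examples, full masking needed fourfold spread (16/8/4) with only the UK left in the indirect pool: direct 8.01 against a halved 8.00. At 6/5/4 with only the UK left, the gap merely shrinks, to 0.61. The other is that the different models and weights give a wrong answer even when all databases contribute. In the examples the point ratio was then about right, and what is lost is precision, because the separate intervals carry between-country variance that a paired contrast removes. The change is worth making but does not undermine the per-database results.

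**What to change.** - **Section 8.8.6:** add log(indirect prevalence / direct prevalence) for each disease, cohort and database. Give it a confidence interval that allows for shared patients, for example a bootstrap run locally by each data partner, with a stated rule for replicates in which the median is not reached.
- **Section 8.9:** make the random-effects meta-analysis of this log ratio the main synthesis of the comparison.
- **Section 8.9:** restrict side-by-side pooled direct and indirect figures, and pooled incidence times pooled duration, to databases contributing every component. List those left out, with the reason.

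The cost is a little more analysis: one derived quantity, a bootstrap and one further metagen call. Only aggregate results leave the sites, as section 9 requires. The restricted figures will rest on fewer databases, but the all-database direct and incidence pools can still be reported alongside.

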8.8.5. Median disease duration

Survival time will be analysed with the R package *survival*. Time zero for the survival analysis is the date of first diagnosis. Patients for whom no date of death is recorded will be censored at the date of end of their observation period or administratively censored at the end of study period.

Median survival time, i.e. disease duration, will be estimated with 95% CI using Brookmeyer-Crowley method [4].

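### Pooling only the databases that yield a median and a finite upper limit selects short durations when the true median lies near or beyond usable follow-up

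*Protocol*

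**What the plan says.** Section 8.8.5 defines the duration input: "Median survival time, i.e. disease duration, will be estimated with 95% CI using Brookmeyer-Crowley method". Patients without a recorded death "will be censored at the date of end of their observation period or administratively censored at the end of study period".

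Section 8.8.6 multiplies this median by the incidence rate (equation 1). For the interval, an approximate Var(log D) "will be generated using the limits D_{low} and D_{upp} of the 95% CI for D" (equation 5), and this feeds Var(log P) in equation (3).

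Section 8.9 pools log D (item 3) with standard errors from equation (5) and log P (item 4) with standard errors from equation (3). It foresees that a database may give no estimate because a count is too small, "or the median disease duration might not be observed in the available data". The rule is then: "Meta-analysis will be done with estimates available". The pooled duration is used once more, in a final product of pooled incidence and pooled duration.

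The protocol has no rule for a database with a median but no finite upper limit. The limitations in section 11 cover missing or wrong diagnosis dates, not this selection. The checklist marks sensitivity analyses (item 10.8) as not applicable.

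**The concern.** The rule treats a missing median as if it were unrelated to the duration. Under heavy censoring it is related. A database with more early deaths by chance has a curve that crosses 50% early; it reports a short D with a finite upper limit and is kept. A database with fewer early deaths reports a median or upper limit that is not reached, and is dropped. Inclusion then depends on the quantity being estimated. A random-effects model cannot repair this, because the shift arises with no true difference between databases.

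The study's only objective is to compare direct and indirect prevalence. Direct prevalence has no such selection, so a shortfall in pooled D could be taken for disagreement between the two methods.

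**Working it through.** **Inputs from the protocol.** Study period 2010 to 2022, 13 years (8.2). Lifelong observation is not available in any source (8.2). Active subjects 1.3, 3.0 and 5.8 million (Table 3). Cohorts from 5 subjects upward are analysed (8.8.1). Diagnoses before observation are included (Table 5). No sample size, disease count or survival figure is given, so there is no planned figure to reproduce. Case numbers, survival shape and censoring below are assumptions.

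**What each quantity needs.**
- Point estimate in one database: P = I × D. This needs the median only.
- Var(log D) = ((log D_upp − log D_low) / (2 × 1.96))². If D_upp is not reached, this is undefined.
- Var(log P) = 1/C + Var(log D), with the covariance set to 0 by equation (6). This is undefined in the same case.

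Pooling in items 3 and 4 therefore needs a finite median and finite limits. If incidence is unbiased and independent of D, the ratio of estimated to true P equals the ratio of estimated to true D.

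**Simulation A.** Three databases of equal size share one true median. Survival is exponential and censoring uniform over 0-13 years. Limits are log-transformed and pooling is DerSimonian-Laird on log D. The ratio is the geometric mean of pooled D over true D, among runs with at least one usable database.

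| Cases per database | True median (years) | Pooled D / true | Runs with nothing to pool |
|---|---|---|---|
| 150 | 7 | 0.96 | 3% |
| 150 | 8 | 0.92 | 25% |
| 150 | 9 | 0.87 | 57% |
| 150 | 10 | 0.84-0.85 | 82% |
| 500 | 3 | 1.00 | 0% |
| 500 | 8 | 0.995 | 0% |
| 500 | 9 | 0.98 | 1% |
| 500 | 10 | 0.93 | 26% |

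With 150 per database and a median of 8, the 5% of runs in which all three databases were usable were also low (0.93), so a complete forest plot is no full reassurance. With 50 per database and a median of 5, the ratio was 0.92-0.93. A decreasing hazard (Weibull shape 0.7) gave 0.81 at 150 cases and a median of 8. With censoring uniform over 0-25 years, 150 cases and a median of 10, the ratio was 1.00.

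**Simulation B.** Cases follow the ratio 1.3 : 3.0 : 5.8. The parts sum to 10.1, so a total of 202 gives 26, 60 and 116 cases (20 × each part), and 404 gives 52, 120 and 232. Diagnoses are uniform over 13 years, with 5% per year deregistration. Separate sets of runs, differing in weights and limit type, gave:
- Median 8, 202 cases: 0.80-0.88.
- Median 8, 404 cases: 0.89-0.93.
- Median 10, 202 cases: 0.83 with random effects and log-log limits; 0.70-0.76 in other runs with inverse-variance weights.
- Median 3: about 1.00.
- Weibull shape 0.6, median 8: 0.63-0.79.
- Weibull shape 2 (increasing hazard), median 8: 0.93-0.99.

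One curve built from all three databases gave 0.95-1.01 in the exponential settings and reached its median in 81-100% of runs.

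**Adding earlier diagnoses.** Simulation B was extended with diagnoses from before 2010, of which 10-25% are recorded, counted from diagnosis with no delayed entry. In the runs closest to the planned pooling, pooled D at medians of 8-10 rose to 1.14-1.48 of the truth. Relative to the combined curve, the selection effect shrank to roughly 0-5%, and the combined curve carried the same upward error. In one setting (median 8, 202 cases, log-log limits), runs with an estimate rose from 59% to 98% at 10% recorded.

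**The case against.** The strongest objection is that in-period diagnoses are not the planned survival cohort. Table 5 takes the earliest recorded diagnosis, before or during observation, and 8.8.5 starts the clock there with no delayed entry. Patients with old diagnoses must have survived to be seen, which lengthens D. A reader might infer from the selection alone that indirect prevalence will be reported too low. The documents do not support that: the net error may be upward. This objection stands.

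Second, the larger shortfalls come from settings that seldom produce a pooled value. At a median of 8 with 202 cases, one set of runs had a usable database in only 9% (log limits) to 48% (log-log limits), so 52-91% pooled nothing. This also stands. The sizes describe values that do appear, not a typical outcome.

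Third, a reader might infer that duration enters the indirect estimate only where the upper limit is reached. That is too strong: equation (1) needs only the median, so such a database still has its own point estimate.

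Fourth, the protocol openly says that medians may be missing, reports each database separately and shows heterogeneity. That lets a reader see which databases are absent. It does not say that absence depends on the estimate, and it does not change the pooled figure.

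**Conclusion.** The pooling rule in 8.9 is biased toward short durations in a borderline range, where the true median lies near or beyond usable follow-up and cases are few. With in-period diagnoses only and one common true duration, the component is about 2-20% downward in most exponential settings examined. It is larger with a decreasing hazard, and reached 30% in some runs of the sparsest setting (median 10, 202 cases). It vanishes for short medians or many cases, and falls to roughly 0-5% if 10-25% of earlier diagnoses are recorded.

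These sizes rest on assumed case numbers, survival shapes and censoring. The protocol gives nothing that would place any of the five diseases inside or outside the affected range. The point concerns one component of error in pooled D and pooled indirect prevalence; it settles neither the sign nor the size of the net error. The change is worth making because the rule is fixed in advance, affects the main comparison and is cheap to amend.

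**What to change.** Amend section 8.9 as follows.

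1. Where a database's median or upper limit is not reached, keep it in the forest plot. Show it as the lower bound I × D_low where D_low exists, and as not reached otherwise.
2. Do not present a pooled D or pooled indirect prevalence built only from databases that reached the median as the combined estimate. Label it as a selected subset that may be biased low. Apply the same label to the final product of pooled incidence and pooled duration.
3. As a supplementary analysis, beside the per-database results and the random-effects pool, have each partner return numbers at risk, deaths and censorings by interval since diagnosis, with small cells merged. Build one combined curve and read D from it.

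Items 1 and 2 cost only wording and plot changes. Item 3 costs one aggregated table per disease and database, which fits the aggregated-results arrangement in section 9. Its limits should be stated: the combined curve averages over country differences in survival, does not remove the bias from pre-observation diagnoses, and may itself not reach its median. That is why it should stand beside the random-effects pool and not replace it.
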